Purpose	To explore the efficacy and safety of IVIEW-1201 (1.0% Povidone Iodine Ophthalmic Gel Forming Sterile Solution) in the treatment of acute bacterial conjunctivitis to provide a basis for the Phase III clinical trial.
Study Design	Mult-center, randomized, parallel-group, positive-controlled.
Criteria	
Inclusion Criteria:
 
Potential study subjects must meet all of the following inclusion criteria to be enrolled in this study.
 
 1. Volunteered to participate in the study and signed the Informed Consent Form after receiving a verbal and written explanation of this clinical trial. In cases where the subject is unable to sign the Informed Consent Form, his/her guardian may sign in accordance with relevant regulations. 2. Aged above 15 (inclusive), male or female. 3. A diagnosis of acute bacterial conjunctivitis based on clinical observations: a) a score of ≥ 1 for bulbar conjunctival congestion and ≥ 1 for conjunctival secretion/exudation in at least one eye (same eye); and b) increased purulent, mucopurulent or mucopurulent secretions are observed in the conjunctival sac of the affected eye in all patients. 
Willing to cooperate in the completion of all procedures and visits required for the trial.
 
Exclusion Criteria:
 
Subjects are excluded from the study if any of the following exclusion criteria are met.
 
 1. Patients with systemic or ocular diseases, or functional disorders with comorbidities, or structural abnormalities that, in the judgment of the investigator, could adversely affect the course or results of the trial (e.g. hyperthyroidism, hepatitis, acute and chronic renal insufficiency). 2. Those who have a history of allergy or serious adverse reactions to any component of IVIEW-1201 (1.0% povidone-iodine ophthalmic gel sterile solution) and Ofloxacin Eye Drops; have a history of allergy or serious adverse reactions to quinolones; or have a cumulative total of three or more allergies to other drugs, food and environment; or who are prone to allergic symptoms such as rash and urticaria; 3. Symptoms or signs of bacterial conjunctivitis for more than 72 hours prior to screening;

	
4. Suspected fungal, viral or acanthamoeba infections based on clinical observations;
 
5. Those with severe keratitis or corneal opacity affecting the study results;
 
6. Active inflammation of the cornea, iris, or anterior chamber;
 
7. Corrected visual acuity of less than 0.2 in either eye;
 
8. History of eye surgery within 3 months prior to screening;
 
9. Those who have a history of acute or chronic dacryocystitis;
 
10. Those who need to wear corneal contact lenses during the trial;
 
11. Those who have used antibiotic eye drops or glucocorticoid eye drops within 14 days, and oral or intravenous antibiotics within 72 hours prior to screening;
 
12. Systemic use of steroidal drugs within 14 days prior to screening. Local use of eye steroidal drugs or nonsteroidal anti-inflammatory drugs (NSAIDs) within 7 days before enrollment (nasally or bronchially inhaled steroidal drugs are not allowed during the study);
 
13. Those with co-infections requiring treatment with other anti-infective drugs in the study;
 
14. Those who are using other drugs that may interfere with the efficacy or safety evaluation of the drug;
 
15. Participation in other interventional clinical trials within 30 days prior to the study;
 
16. Pregnant or lactating women, women with positive pregnancy tests and those planning to become pregnant (including male subjects); subjects who do not take effective contraceptive measures within 1 month before enrollment, or subjects (including male subjects) who are unwilling to take effective contraceptive measures within the next 6 months.
 
17. Other conditions or illnesses judged by the clinical investigator to be unsuitable for enrollment.

Sample Size	120 cases, 60 cases in the treatment group and 60 cases in the control group.
Investigational Drug	IVIEW-1201 (1.0% Povidone Iodine Ophthalmic Gel Forming Sterile Solution): usually a reddish brown thick liquid or gel, which becomes a brown uniform transparent solution after shaking. Specification: 5g: 5mg (based on I2), Bio-Concept Laboratorie (USA)
Comparator Drug	Ofloxacin Eye Drops (Tarivid®) Slightly yellowish green clear solution, specification: 5ml:15mg, Santen Pharmaceutical (China) Co., Ltd.
Administration Method	
IVIEW-1201
 
Shake well before use, 1 drop/eye/time in the affected eye. The drug shall be administered once at the study site on Day 1, and then at least once every 3 hours until bedtime, up to a maximum of 4 doses; The drug shall be administered 4 doses on Day 2, with an interval of at least 3 hours; The drug shall be administered 3 doses a day from Day 3 to Day 7, with an interval of at least 3 hours, with duration of administration of 7 days.
 
Ofloxacin Eye Drops (Tarivid®)
 
Shake well before use, 1 drop/eye/time in the affected eye. The drug shall be administered once at the study site on Day 1, and then at least once every 3 hours until bedtime, up to a maximum of 4 doses; The drug shall be administered 4 doses on Day 2, with an interval of at least 3

	
hours; The drug shall be administered 3 doses a day from Day 3 to Day 7, with an interval of at least 3 hours, with duration of administration of 7 days.
 
Administration Route
 
Sit or lie on back, tilt head back slightly, look up, place the test drug bottle mouth close to the eyelid of the affected eye, drop 1 drop, then gently close eyes and press the inner canthus of the eye with fingers for 1 to 2 minutes, then rest for about 5 minutes. If the test drug is not completely dropped into the eye during administration, add one drop. Among them, the test group needs to gently shake the drug solution before instilling it before use.


Treatment of Newly Infected eyes
	
If a subject suffers from monocular disease at Visit 1 and the other healthy eye becomes infected and develops bacterial conjunctivitis after Visit 1 during the study, the newly infected eye shall be treated with the investigational drug of the subject's group, following the prescribed administration regimen for the group, i.e. "the drug shall be administered once in the study site on Day 1, and then at least once every 3 hours until bedtime, up to a maximum of 4 doses; the drug shall be administered 4 doses on Day 2, with an interval of at least 3 hours; the drug shall be administered 3 doses a day from Day 3 to Day 7, with an interval of at least 3 hours, with duration of administration of 7 days", until Visit 5. At Visit 5, if the investigator determines that the newly infected eye still requires continued treatment based on the subject's signs and symptoms, the investigator will determine the specific treatment regimen after the subject is removed from the study, but the use of IVIEW-1201 (1.0% povidone-iodine ophthalmic gel sterile solution) should be discontinued. Newly infected eyes are not included in the group test, but normal secretions are taken for bacterial culture.

Visits
	
This study will be divided into 5 visit phases, namely Visit 1 (screening/baseline period, Day 1), Visit 2 (Day 3), Visit 3 (Day 6), Visit 4/End of Treatment(EOT) (Day 8 ±1 day) and Visit 5/End of Study(EOS) (Day 14±1 day).


Efficacy Evaluation
	
Primary outcomes
 
Clinical cure rate: The proportion of subjects with a score of 0 (on a 3-point scale) for bulbar conjunctival congestion and 0 (on a 3-point scale) for conjunctival secretion/exudation at Visit 4 (Day 8±1 day) and Visit 5 (Day 14±1 day).
 
Secondary outcomes
 
Clearance rate: The clearance rate of each major pathogenic bacteria at Visit 2, 3, 4 and 5: Stratified analysis shall be conducted according to the type of pathogenic bacteria and the visit time point, and the clearance rate of each kind of bacteria by the investigational drug at different times shall be calculated. Bacterial clearance is defined as positive bacterial culture at baseline and negative bacterial culture at the last visit. Bacterial clearance rate = (number of subjects cleared + number of subjects assumed to be cleared) / total number of subjects enrolled × 100%.
 
Exploratory outcomes
 
Mean clinical improvement rate at Visit 2, 3, 4 and 5:
 
Clinical improvement rate = (pre-treatment score - post-treatment score) / pre-treatment score x

	
100%. The score of symptoms and signs is the sum of the scores for pain, foreign body sensation, photophobia, tearing, conjunctival congestion, conjunctival secretion/exudation and conjunctival edema.
 
Total effective rate (%) at Visit 2, 3, 4 and 5:
 
Total effective rate (%) = (number of subjects cured+ number of subjects markedly effective) / total number of subjects available for evaluation of efficacy $\times 100\%$. Comprehensive efficacy evaluation: defined as cured, markedly effective, effective and ineffective; Calculate the total effective rate; See Appendix 2 for judgment criteria.

Safety Evaluation	
Including adverse events/serious adverse events, clinically significant changes in ocular and systemic symptoms and signs before and after treatment.

Statistical analysis method	
Selection of statistical analysis data set
 
Full Analysis Set (FAS): All subjects randomized and for whom the data of at least one post-dose efficacy indicator is collected. Only the following randomized subjects are excluded: Subjects who violates key eligibility criteria, who are not treated with the investigational drug, and who have no observed data after randomization.
 
Per Protocol Set (PPS): A subset of the FAS, excluding subjects with significant protocol violations that may affect the primary efficacy evaluation based on the FAS.
 
Safety Set (SS): All subjects who have used the study drug at least once.
 
The efficacy analysis is mainly based on the FAS, but also on the PPS; the SS is used for safety analysis.
 
Statistical analysis method
 
This study will use SAS software version 9.4 or above for statistical analysis.
 
The statistical description of quantitative indicators will calculate the number of subjects, mean, standard deviation, median, minimum and maximum (25% quantile Q1, 75% quantile Q3 where necessary), the statistical description of categorical indicators will calculate the number of subjects and percentage.
 
The T-test or non-parametric comparison is used for inter-group comparison of quantitative indicators, and the chi-square test or Fisher's exact probability method is used for inter-group comparison of categorical indicators.
 
Statistical analysis and methods
 
Efficacy analysis
 
Statistical analysis of the primary efficacy indicators and secondary indicators for comparison between groups is performed based on the FAS and PPS respectively.
 
Primary efficacy indicators: The clinical cure rate of each group is counted and compared using the χ^2 test or Fisher's exact probability method.
 
Secondary efficacy indicators: fungal clearance and change in best-corrected visual acuity will be calculated based on the target eye. In addition, pain improvement and clinical effective rate will be described and compared between groups.

	
Safety analysis
 
Adverse event: Treatment-Emergent Adverse Event (TEAEs) should be focused on, i.e. treatment-emergent adverse events. The χ^2 test or Fisher's exact probability method is used to compare the incidence of adverse events in each group and the incidence of adverse events related to the study drug. All adverse events will be coded using the Medical Dictionary for Regulatory Activities (MedDRA) and the number of cases, incidence and frequency of each type of adverse event occurring during the trial will be summarized by SOC/PT. The adverse events occurring in this trial will be tabulated and described.

--	---

Overview of study flow chart of IVIEW 1201

Visit schedule	Visit 1	Visit 2	Visit 3	Visit 4/ EOT	Visit 5/ EOS
Test stage	Screening/Baseline/Day 1	Day 3	Day 6	Day 8	Day 14/ Early withdrawal
Visit window period				(± 1 days)	(± 1 days)
Signing of Informed Consent Form	X				
Inclusion and exclusion criteria	X				
Randomization	X				
Demographic data ¹	X				
History taking ²	X				
Subjective Symptoms Score ³	X	X	X	X	X
Objective Clinical Score ⁴	X	X	X	X	X
Collection of conjunctival sac secretion ⁵	X	X	X	X	X
Vital signs ⁶	X	X	X	X	X
Pregnancy Test ⁷	X				X
Corneal endothelial cell count	X				X
Best-corrected visual acuity	X	X	X	X	X
Corneal fluorescein staining	X	X	X	X	X
Slit-lamp examination	X	X	X	X	X
Intraocular pressure measurement	X	X	X	X	X
Fundus examination	X				X
12-lead ECG examination	X				
Drug allocation ⁹	X				
Study drug administration ¹⁰	X	X	X		
Drug compliance assessment		X	X	X	
Recoding of concomitant medications	X	X	X	X	X
Adverse events ¹¹	X	X	X	X	X
Check of diary card		X	X	X	
Return of drugs				X	X

1.Demographic information: date of birth, gender, ethnicity, height, weight.

2.Medical history collection: including past medical history, surgical history, current medical history (time of onset, cause, etc.), comorbidities, medication history, etc. Any clinically significant examination results other than the research disease found during the screening period should be recorded as medical history.

3.Symptom scoring: Four symptoms (pain, foreign body sensation, photophobia, and tearing) were scored using a 3-point scale (0 = none, 1 = mild, 2 = moderate, 3 = severe). Under the guidance of the researchers, the subjects scored according to the actual situation on the day before the visit and checked in the record form.

4.Sign scoring: The three signs (conjunctival congestion, conjunctival secretion/exudation, and conjunctival edema) were scored using a 3-point scale (0 = none, 1 = mild, 2 = moderate, and 3 = severe); the researchers examined and recorded them.

5. Collection of conjunctival sac secretions: Preparation before sampling: Collect bacterial culture tubes and sterile swabs provided by the central laboratory. When sampling, fully expose the bulbar conjunctiva and fornix conjunctiva, and use a sterile swab moistened with sterile 0.9% sodium chloride solution to gently swab the surface of the conjunctival sac 4 times from the inner canthus from the inside to the outside (pay attention not to miss the inner canthus, and collect the dense secretions), avoid contact with eyelashes and eyelid margins, and use eyelid openers and other instruments when necessary. After sampling, place the specimen in a sterile transport tube, mark it, and send it to the hospital laboratory for bacterial culture. All subjects need to take secretions from both eyes for bacterial culture, and indicate the subject number and eye type.

6.Vital signs: including body temperature, heart rate, blood pressure, etc.

7.Pregnancy test: For women of childbearing age, blood/urine pregnancy test can be accepted (blood pregnancy test is the main method, if it is not met, urine pregnancy test can be selected).

8.The investigators will determine whether mydriasis is required for fundus examination. If mydriasis is required, mydriasis should be applied after secretions are collected for relevant examinations. Fundus examination or fundus photography can be accepted.

9.Medication distribution: According to the medication plan, the drugs will be distributed to the subjects. These drugs will be taken by the patients themselves or with the help of caregivers or the trial team for 7 days from D1 to D7.

10.After randomization of the subjects who meet the criteria at Visit 1, the staff of the Clinical Research Center will distribute the study drugs, and then start to instruct the subjects on the topical eye drops as soon as possible and supervise the first administration. After that, the subjects will self-administer the drugs according to the dosing regimen. On the day of Visit 2 and Visit 3, the study drugs shall not be used within 1 hour before the visit.

11.Adverse events refer to all adverse medical events that occur to subjects after the first medication. However, in order to protect the rights and interests of the subjects, the recording of adverse events in this study starts from the signing of the informed consent form.

12. After completing Visit 4, IVIEW-1201 (1.0% povidone-iodine eye gel sterile solution) needs to be discontinued. If the investigator determines that treatment is still needed based on the subject's symptoms and signs, the specific treatment plan will be determined by the investigator, and the subject needs to continue in the group until Visit 5 (Day 14±1).

ABBREVIATIONS

AE	Adverse Event
TEAE	Treatment-Emergent Adverse Event
CTCAE	Common Terminology Criteria for Adverse Events
CRF	Case Report Form
D	Day
EC	Ethics Committee
EDC	Electronic Data Capture System
eCRF	Electronic Case Report Form
EOS	End of Study
EOT	End of Treatment
FAS	Full Analysis Set
FDA	Food and Drug Administration
GCP	Good Clinical Practice
MedDRA	Medical Dictionary for Regulatory Activities
NSAID	Nonsteroidal Anti-inflammatory Drugs
PVP-I	Povidone Iodine
PPS	Per Protocol Set
Q1	25% quantile
Q3	75% quantile
SAE	Serious Adverse Event
SS	Safety Set
VAS	Visual Analogue Scale
BCVA	Best-corrected visual acuity
MRSA	Methicillin-resistant Staphylococcus aureus
IWRS	Interactive Web Response System
ETDRS	Early Treatment Diabetic Retinopathy Study

1. Introduction

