2.2.3 Exploratory Endpoints

Mean clinical improvement rate at Visit 2, 3, 4 and 5:

Clinical improvement rate = (pre-treatment score - post-treatment score) / pre-treatment score × 100%. The score of symptoms and signs is the sum of the scores for pain, foreign body sensation, photophobia, tearing, conjunctival congestion, conjunctival secretion/exudation and conjunctival edema.

Total effective rate (%) at Visit 2, 3, 4 and 5:

Total effective rate (%) = (number of subjects cured+ number of subjects markedly effective) / total number of subjects available for evaluation of efficacy × 100%. Comprehensive efficacy evaluation: defined as cured, markedly effective, effective and ineffective; Calculate the total effective rate; See Appendix 2: Evaluation criteria of comprehensive efficacy for judgment criteria.

3. Trial Design

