3.1 Overall Design

A multi-center, randomized, parallel, positive drug-controlled study design is used. In this study, the test drug IVIEW-1201(1.0% povidone-iodine ophthalmic gel sterile solution) is selected for the test group and the positive control drug Ofloxacin Eye Drops is selected for the control group. There are a total of 120 subjects: 60 in the test group and 60 in the control group.

The subject population in this study are those aged 15 and above (inclusive) with a confirmed diagnosis of acute bacterial conjunctivitis. Subjects should complete the random allocation and initial administration of the investigational drug on the day of diagnosis.

This study will be divided into 5 visit phases, namely Visit 1 (screening/baseline period, Day 1), Visit 2 (Day 3), Visit 3 (Day 6), Visit 4/End of Treatment(EOT) (Day 8 ±1 day) and Visit 5/End of Study(EOS) (Day 14±1 day).

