3.5 Blinding

In this study, there are significant differences between the investigational drug and the positive control drug in color, taste, properties and the patient's feeling when applying the medicine. The patient can easily distinguish them, which make it very easy to break the blind. Therefore, a single-blind or blind subject design cannot be used. The excipient components of ofloxacin placebo are unknown and too difficult to obtain for a double-blind double-simulation design. Since there are marketed drugs with clear efficacy for acute bacterial conjunctivitis, there are ethical issues in using a double-blind design with a placebo of 1.0% povidone-iodine eye gel sterile solution as a control.

The study is a blinded (assessor) study design. This means that the investigators are authorized to be blinded and non-blinded. Blinded and non-blinded team members shall be relatively independent in their work, limiting non-essential communication and avoiding disclosure of blind information.

Blindness shall be established when subjects are randomized. Blindness should be maintained until the blinded data review is completed, the database is locked and the primary statistical analysis is completed; The scope of the maintenance includes the above evaluators and blinded data analysts. The unblinding will be performed after the blinded data review is completed and the database is locked, and will be performed twice through the operation of the central randomization system. The first unblinding shall be performed after the database is locked, and the unblinding area is divided into groups X and Y and sent to the blinded data analysts for statistical analysis; The second unblinding shall be performed after the completion of the primary statistical analysis, and the specific test group or positive control drug group corresponding to groups X and Y shall be determined.

4. Selection of Subject

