4.2 Exclusion Criteria

Subjects are excluded from the study if any of the following exclusion criteria are met.

1. Patients with systemic or ocular diseases, or functional disorders with comorbidities, or structural abnormalities that, in the judgment of the investigator, could adversely affect the course or results of the trial (e.g. hyperthyroidism, hepatitis, acute and chronic renal insufficiency).
2. Those who have a history of allergy or serious adverse reactions to any component of IVIEW-1201 (1.0% povidone-iodine ophthalmic gel sterile solution) and Ofloxacin Eye Drops; have a history of allergy or serious adverse reactions to quinolones; or have a cumulative total of three

or more allergies to other drugs, food and environment; or who are prone to allergic symptoms such as rash and urticaria;

3. Symptoms or signs of bacterial conjunctivitis for more than 72 hours prior to screening.
4. Suspected fungal, viral or acanthamoeba infections based on clinical observations;
5. Those with severe keratitis or corneal opacity affecting the study results;
6. Active inflammation of the cornea, iris, or anterior chamber;
7. Corrected visual acuity of less than 0.2 in either eye;
8. History of eye surgery within 3 months prior to screening;
9. Those who have a history of acute or chronic dacryocystitis;
10. Those who need to wear corneal contact lenses during the trial;
11. Those who have used antibiotic eye drops or glucocorticoid eye drops within 14 days, and oral or intravenous antibiotics within 72 hours prior to screening;
12. Systemic use of steroid drugs within 14 days prior to screening. Local use of eye steroid drugs or nonsteroidal anti-inflammatory drugs (NSAIDs) within 7 days before enrollment (nasally or bronchially inhaled steroid drugs are not allowed during the study);
13. Those with co-infections requiring treatment with other anti-infective drugs in the study;
14. Those who are using other drugs that may interfere with the efficacy or safety evaluation of the drug;
15. Participation in other interventional clinical trials within 30 days prior to the study;
16. Pregnant or lactating women, women with positive pregnancy tests and those planning to become pregnant (including male subjects); subjects who do not take effective contraceptive measures within 1 month before enrollment, or subjects (including male subjects) who are unwilling to take effective contraceptive measures within the next 6 months.

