6.5 Indicators

6.5.1 Indicators of clinical cure rate

6.5.1.1 Subjective Symptoms Score

- Pain: according to the subjective feelings of subjects, a 3-score scale is used (0=none, 1=mild, 2=moderate, 3=severe)
- Sensation of foreign body: according to the subjective feelings of subjects, a 3-score scale is used (0=none, 1=mild, 2=moderate, 3=severe)
- Photophobia: according to the subjective feelings of subjects, a 3-score scale is used (0=none, 1=mild, 2=moderate, 3=severe)

- Weep: according to the subjective feelings of subjects, a 3-score scale is used (0=none, 1=mild, 2=moderate, 3=severe)

See Appendix 1: Symptom Scoring Criteria for specific scoring criteria.

6.5.1.2 Objective Clinical Score:

- Scores of conjunctival hyperemia: Score the conjunctival hyperemia of the palpebral conjunctiva and bulbar conjunctiva respectively, using a 3-point scale (0= none, 1= mild, 2= moderate, 3= severe) to score the conjunctival hyperemia;
- Scores of conjunctival secretions/exudation: A 3-point scale (0= none, 1= mild, 2= moderate, 3= severe) is used to score conjunctival secretions.
- Scores of conjunctival edema: A 3-point scale (0= none, 1= mild, 2= moderate, 3= severe) is used to score conjunctival edema.

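### Flow-chart footnote 3 scores symptoms for the day before each visit and signs at the visit, so the summed score mixes two days, can start from a pre-onset baseline, and reflects dosing days on treatment

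*Combined protocol and SAP*

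**What the plan says.** Footnote 3 of the study flow chart covers pain, foreign body sensation, photophobia and tearing, each scored 0 to 3. It states that "the subjects scored according to the actual situation on the day before the visit and checked in the record form". The row it belongs to is marked at all five visits, including Visit 1.

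Footnote 4 covers the three signs and says only that "the researchers examined and recorded them". Sections 6.1 to 6.4 list both scores among the procedures of each visit, with no look-back period. Section 6.5.1.1 gives none either ("Pain: according to the subjective feelings of subjects, a 3-score scale is used"), nor does Appendix 1. Nothing elsewhere repeats or overrides footnote 3.

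Section 2.2.3 combines the two sets of items: "The score of symptoms and signs is the sum of the scores for pain", the other three symptoms and the three signs. The clinical improvement rate is the percentage fall in that sum from the pre-treatment value. Appendix 2 grades subjects by percentage reduction in the symptom and sign scores.

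On timing, section 3.1 requires that "Subjects should complete the random allocation and initial administration of the investigational drug on the day of diagnosis". Section 4.2 excludes "Symptoms or signs of bacterial conjunctivitis for more than 72 hours prior to screening" and sets no lower limit. Footnote 10 adds: "On the day of Visit 2 and Visit 3, the study drugs shall not be used within 1 hour before the visit". Section 3.5 explains that subjects cannot be blinded because the products differ in "color, taste, properties and the patient's feeling when applying the medicine".

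**The concern.** A composite change score needs its parts to describe the same moment, and its baseline to describe the disease being treated. Footnote 3, followed as written, can fail on both.

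At Visit 1 the symptom items describe the day before enrolment. For someone who fell ill on Day 1, that day was symptom-free. The baseline composite is then too low, and every later percentage reduction is understated or turns negative.

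On treatment the symptom items describe a day on which drops were instilled several times. The arms differ in how the drops feel and subjects know which product they have, so recalled symptoms may partly reflect the drops and not the infection. The dose-free hour in footnote 10 applies on the visit day and cannot protect a score that refers to the day before.

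At stake are the exploratory improvement rate and total effective rate at Visits 2 to 5, and the pain improvement and clinical effective rate that section 10.3.4 lists under secondary indicators and compares between groups. These results are meant to inform Phase III.

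**Working it through.** The plan gives no figure for this point, so there is none to reproduce. The check is a calendar check followed by two illustrations on assumed values.

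**1. Which day is scored.** Symptom day = visit day - 1. Visit days are from section 3.1 and scheduled doses from section 5.4.

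| Visit | Visit day | Symptom day | Scheduled doses that day |
|---|---|---|---|
| 1 | 1 | day before Day 1 | 0 |
| 2 | 3 | 2 | 4 |
| 3 | 6 | 5 | 3 |
| 4 | 7, 8 or 9 | 6, 7 or 8 | 3, 3 or 0 |
| 5 | 13 to 15 | 12 to 14 | 0 |

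Visits 2 and 3, and Visit 4 at its nominal Day 8, all score full dosing days. Within the Visit 4 window, some subjects score a dosing day and others a day off drug.

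**2. Weight of the symptom items.** Symptoms 4 x 3 = 12 points; signs 3 x 3 = 9 points (congestion counted as one item); total 21. Symptoms are 12 of the 21 points.

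**3. Can the denominator be zero?** Inclusion criterion 3 requires congestion of at least 1 and secretion of at least 1, so the composite baseline is at least 1 + 1 = 2. It is never zero. A pain-only or symptom-only percentage is undefined when that baseline is 0.

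**4. Effect on the improvement rate.** Formula: (pre - post) / pre x 100. Assumed scores: baseline signs 5; true Day 1 symptoms 6; composite 7 at Visit 2 (symptoms 4, signs 3) and 1 at Visit 4. Later scores are held fixed so that only the baseline varies, and Appendix 2 cut-offs are applied to the composite.

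| Baseline symptoms | Baseline composite | Visit 2 | Visit 4 |
|---|---|---|---|
| 6 (visit day) | 11 | (11-7)/11 = +36.4%, effective | (11-1)/11 = 90.9%, cured |
| 3 (previous day) | 8 | (8-7)/8 = +12.5%, ineffective | (8-1)/8 = 87.5%, markedly effective |
| 0 (pre-onset) | 5 | (5-7)/5 = -40.0%, ineffective | (5-1)/5 = 80.0%, markedly effective |

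The total effective rate counts cured plus markedly effective, so it does not change in this Visit 4 example; nor at Visit 2, where no row reaches 70%. It can change for other scores. A 70% reduction requires a composite of at most 0.3 x 11 = 3.3 from a baseline of 11, but at most 0.3 x 5 = 1.5 from a baseline of 5. A later composite of 2 or 3 therefore counts in the first case and not in the second.

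**5. How many subjects.** Assume onset is uniform over the permitted 0 to 72 hours. The share with onset after the scored day ended is visit clock hour / 72: 8/72 = 11.1% at 08:00, 12/72 = 16.7% at midday, 16/72 = 22.2% at 16:00. Of 120 subjects, that is about 13 to 27. The documents give no onset distribution.

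**The case against.** The strongest objection is to the reading itself. The previous-day rule stands in one translated footnote, and Appendix 1 words the pain scale as if the subject marks current pain. The sponsor may have meant on the day, before the visit. This stands as a reason for medium confidence. It does not remove the point, since sites will work from the written words and nothing else in the protocol corrects them. That signs are scored on the visit day is also an inference, from footnote 4 and sections 6.1 to 6.4, though no other reading fits well.

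A reader might infer several stronger things that the documents do not support:

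- *That the main result is compromised.* The primary endpoint uses two signs only, and the bacterial clearance endpoint rests mainly on culture and does not use the symptom scores.
- *That the baseline error favours one arm.* It arises before treatment, so 1:1 randomisation balances it in expectation. It adds noise and shifts the rates in both arms.
- *That a third of subjects are affected, from 24/72 = 33% with onset within 24 hours.* Someone with onset the previous afternoon did have symptoms on the scored day. Even 11% to 22% may be high: entry needs purulent or mucopurulent secretion, and section 1.1 says secretions are mucous at first.
- *That instillation discomfort is known to distort the scores.* Section 3.5 says the products feel different and subjects can tell them apart. It reports no pain or tearing and no duration, so a differential effect is possible but not shown.

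The -40% example is the extreme case; a previous-day score of 3 gives +12.5%. Scoring a whole day also has some merit for symptoms that fluctuate.

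**Conclusion.** The point holds as a measurement defect of limited reach, with medium confidence. As written, footnote 3 pairs previous-day symptoms with visit-day signs in one sum. It allows a pre-onset symptom baseline for subjects who present on the day of onset, and it scores dosing days at Visits 2 and 3 and at a nominal Visit 4.

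The baseline part lowers or reverses individual improvement rates, and its frequency rests on the uniform-onset assumption. It is not a bias between arms. The on-treatment part is the one that could differ by arm, and the documents allow no estimate of its size. Division by zero is confined to pain-only or symptom-only percentages. It could still occur with visit-day scoring, because entry requires no minimum symptom score. The change is worth making because it is cheap, not because the trial's main conclusion depends on it.

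**What to change.** In footnote 3, section 6.5.1.1, Appendix 1 and the record form, state once and consistently that the four symptoms are scored for how the eye feels at the visit, before any diagnostic drop and, at Visit 1, before the first dose. Symptoms and signs then refer to the same time in both arms. At Visits 2 and 3 the interval already in footnote 10 then covers the symptom scores too. That interval does not extend to Visit 4, so for a Visit 4 that falls on a dosing day, record the time since the last dose. If on the day, before the visit was the intended meaning, correct the translation to say so.

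The cost is a sentence in each place and a revised record form, with no added visit or procedure. The downside is that symptoms that come and go during the day are captured at one moment only. Subjects remain unblinded, so the change removes the timing problem but not the reporting bias that open treatment can bring.
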